9.4.2.1. Guidance for Cardiac Monitoring Following Treatment Initiation or Re-Initiation

Prerandomization (ie, pre-dose/baseline) full vital signs (resting heart rate, systolic and diastolic BP, body temperature, and respiratory rate) and a 12-lead ECG (taken with the subject in the supine position) will be assessed and used as the baseline measurement. The lowest pre-dose heart rate measurement using vital signs will be used for comparison to the post-dose measurement. After confirming enrollment eligibility, a Holter monitor will be placed on subjects prior to treatment administration. Subjects should receive the first dose of study treatment before 12:00 PM (noon). First Dose Cardiac Monitoring will begin upon treatment administration.

Holter Recording

Holter recording will be conducted in addition to First Dose Cardiac Monitoring if/when available and where allowed by regulatory authorities and local ethics committees.

At the Week 0/Day 1 visit (Table 6), once eligibility is confirmed, a Holter monitor will be placed on the subject at the study site and continuous Holter recording should begin approximately 15 minutes before first administration of study treatment. If the subject meets the discharge criteria after cardiac monitoring in < 8 hours following the first administration of study treatment, the subject will be discharged from the study site with the Holter monitor in place and continue to wear the Holter monitor until Hour 8 (± 15 minutes) post-treatment administration.

Subjects will be instructed on how to remove the Holter monitor at Hour 8 (\pm 15 minutes) and to return the device for analysis at the next in-person study visit. If the subject requires extended in-clinic cardiac monitoring \geq 8 hours, the Holter will be removed onsite at Hour 8 (\pm 15 minutes), prior to discharge.

Additional details about the Holter recording procedure will be provided in the Holter Manual and subject instructions.

First Dose Cardiac Monitoring

In-clinic cardiac monitoring, of at least 4 hours, will occur on Day 1 and will include the following (Table 2):

- After the first administration of study treatment on Day 1, subjects must remain under observation in the clinic for at least 4 hours.
- At Hours 1, 2, and 3 (± 15 minutes) post-dose, the heart rate and systolic and diastolic BP will be assessed with the subject in the sitting position, with the time recorded. If the subject has a heart rate < 50 bpm or if cardiovascular symptoms develop, then the subject should remain closely monitored, including 12-lead ECGs as clinically indicated, until the Hour 4 discharge assessment.
- At the Hour 4 (± 15 minutes) discharge assessment, heart rate and systolic and diastolic BP will be assessed with the subject in the sitting position and a 12-lead ECG (with the subject in the supine position) will be performed. Subjects may be discharged from the clinic after the 4-hour assessment if they meet the criteria described in Table 3. Subjects not meeting the discharge criteria will require extended monitoring as described below.
- Subjects experiencing a clinically relevant treatment-related symptomatic event (eg, chest pain, dizziness, palpitations, or syncope) associated with reduction of the heart rate or clinically relevant 12-lead ECG changes at any time during the 4-hour monitoring period must be discontinued from treatment (Table 4).

Table 2: Procedures to be Performed During the Monitoring Period

Procedure	Pre-dose	Hours 1, 2, 3 Post-dose ^a	Hour 4 Post-dose ^a
Blood pressure and heart rate ^b	x	x	х
12-lead ECG	х		х
Assess discharge criteria			х

^a Measurements may be taken ± 15 minutes of the scheduled time.

ECG, electrocardiogram

Table 3: Discharge Criteria After Cardiac Monitoring

Subjects will be released from the clinical site after dosing on Day 1 (but no sooner than 4 hours post-dose) when they fulfill the following discharge criteria:

- Heart rate ≥ 50 bpm or no more than 10 bpm lower than the pre-dose (baseline) value
- No evidence of second-degree AV block or higher
- No cardiac symptoms (eg, chest pain, dizziness, palpitations, lightheadedness, shortness of breath, or syncope)

Note: Subjects should have written instructions on when to return to the clinic and a 24-hour contact phone number to call in the event of any new or worsened cardiovascular symptoms.

AV, atrioventricular; bpm, beats per minute

b Heart rate is based on vital signs.

Extended Cardiac Monitoring

Subjects who do not meet discharge criteria at 4 hours post-dose will require extended cardiac monitoring:

- Vital signs will be assessed hourly and 12-lead ECG may be performed, as clinically indicated, until the subject meets the discharge criteria (Table 3).
- The Medical Monitor should be contacted if the subject does not meet the discharge criteria after ≥ 4 hours of extended cardiac monitoring (ie, approximately 8 hours after dosing).
- Any subject who requires extended monitoring on Day 1 must return on Day 2 for the second dose and will be re-monitored as on Day 1, including 8-hour Holter recording (refer to Section 9.9.4). Subjects will be discontinued from study treatment if they do not meet the discharge criteria at 4 hours after the second dose on Day 2. For the safety of the subject, extended cardiac monitoring should be continued until the subject meets the discharge criteria (Table 3).
- Subjects experiencing a symptomatic event (eg, chest pain, dizziness, palpitations, lightheadedness, shortness of breath, or syncope) at any time during the 4-hour monitoring period on Day 1 that is not associated with either a reduction in heart rate or clinically relevant change in 12-lead ECG, may be discharged provided they meet the discharge criteria (Table 3), and as deemed appropriate by the Investigator; however, these subjects must return on Day 2 for the second dose and will be re-monitored as on Day 1. These subjects must be discontinued from treatment if they do not meet the discharge criteria at 4 hours after the second dose on Day 2 and extended cardiac monitoring should be continued until the subject meets the discharge criteria (Table 3).

Study Treatment Discontinuation Related to Post-Dose Cardiac Monitoring

A complete list of reasons for study treatment discontinuation is provided in Section 5.1. Reasons for study treatment discontinuation specific to post-dose cardiac monitoring are provided in Table 4. The Medical Monitor should be contacted before discontinuing a subject.

Table 4: Discontinuation of Study Treatment Related to Post-Dose Cardiac Monitoring

Reasons for Study Treatment Discontinuation Related to Post-dose Cardiac Monitoring a

- Subjects who have a cardiovascular treatment-related symptomatic event (eg, chest pain, dizziness, palpitations, lightheadedness, shortness of breath, or syncope) associated with reduction of the heart rate or associated with clinically relevant 12-lead ECG changes at any time during the 4-hour monitoring period on Day 1 or Day 2 (as applicable).
- Subjects who have not met the discharge criteria on Day 1 after ≥ 4 hours of extended monitoring, or Day 2 by 4 hours post-dose.

All treatment discontinuations should be discussed with the Medical Monitor. ECG, electrocardiogram

Cardiac Monitoring Upon Treatment Re-Initiation Following Dose Interruption

Subjects should undergo the same First Dose Cardiac Monitoring procedures as the original treatment initiation when study treatment dosing is re-initiated after interruption for:

- ≥ 2 consecutive days within the first week of treatment
- ≥ 7 consecutive days after the first week of treatment

Holter recording will not be repeated for treatment re-initiation.

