5. REMOVAL OF SUBJECTS FROM STUDY TREATMENT OR ASSESSMENT

5.1. Discontinuation from Study Treatment

A subject's double-blind treatment may be discontinued for any of the following reasons:

- Worsening of disease (Note: If a subject discontinues double-blind treatment at any time starting with the Week 12 assessment, the subject may be eligible to enter the APD334-303 OLE study [Section 5.1.1])
- Adverse event that in the judgement of the Investigator and/or Medical Monitor the subject should not continue study treatment
- Subject noncompliance with the protocol or study treatment that is considered significant by the Medical Monitor
- Investigator decision
- Withdrawal by subject or parent/guardian (if applicable)
- Lack of efficacy
- Lost to follow-up
- Study termination by Sponsor
- Other, non-adverse event

A subject's double-blind treatment must be discontinued for any of the following reasons:

- Decline in PFT values (FEV₁ and/or FVC) below 50% of the predicted values
- Confirmed diagnosis of clinically significant macular edema
- Confirmed diagnosis of active TB
- Subjects who have a cardiovascular treatment-related symptomatic event (eg, chest pain, dizziness, palpitations, lightheadedness, shortness of breath, or syncope) associated with reduction of the heart rate or associated with clinically relevant ECG changes at any time during the 4-hour monitoring period on Day 1 or Day 2 (as applicable) (Section 9.4.2.1)
- Subjects who have not met the discharge criteria on Day 1 after ≥ 4 hours of extended monitoring, or Day 2 by 4 hours post-dose (Table 3).
- Pregnancy (Section 9.9.10)
- Suspected drug induced liver injury as defined by the 2009 FDA Guidance for Industry (FDA 2009)

- ALT or AST > 8 × ULN
- ALT or AST > 5 × ULN for > 2 weeks
- ALT or AST > 3 × ULN and (total bilirubin > 2 × ULN or international normalized ratio > 1.5)
- ALT or AST > 3 × ULN with the appearance of fatigue, nausea, vomiting, right upper quadrant pain or tenderness, fever, rash, and/or eosinophilia (> 5%)

Because transient fluctuations of ALT or AST are common, and progression to severe drug-induced liver injury or acute liver failure is uncommon, automatic discontinuation of study treatment upon finding a greater than 3 × ULN elevation of ALT or AST may be unnecessary. If a drug-induced liver injury is identified, refer to Appendix 6 for guidance.

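### The Day 2 redosing instruction in Protocol 9.4.2.1 has no exception for subjects whom Section 5.1 and Table 4 require to stop treatment on Day 1

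*Protocol*

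**What the plan says.** Protocol 9.4.2.1 sends everyone who fails the Table 3 discharge criteria at Hour 4 into extended monitoring: "Subjects not meeting the discharge criteria will require extended monitoring as described below". Three bullets under Extended Cardiac Monitoring then matter here:

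- For subjects still failing at about Hour 8: "The Medical Monitor should be contacted if the subject does not meet the discharge criteria after ≥ 4 hours of extended cardiac monitoring". This bullet does not say that treatment stops.
- The Day 2 bullet: "Any subject who requires extended monitoring on Day 1 must return on Day 2 for the second dose". The subject is then monitored again as on Day 1, with an 8-hour Holter recording, and is discontinued if the criteria are not met 4 hours after the second dose.
- A further bullet sends some symptomatic subjects back on Day 2, but only after an event "that is not associated with either a reduction in heart rate or clinically relevant change in 12-lead ECG".

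Section 5.1 states that a subject's "double-blind treatment must be discontinued for any of the following reasons". Two of the reasons listed concern Day 1:

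- **Stop A:** "Subjects who have not met the discharge criteria on Day 1 after ≥ 4 hours of extended monitoring".
- **Stop B:** a treatment-related cardiovascular symptomatic event, within the 4-hour monitoring period, accompanied by a lower heart rate or clinically relevant ECG changes.

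Table 4, in the same subsection as the Day 2 bullet, lists both stops, and the text above it says: "Reasons for study treatment discontinuation specific to post-dose cardiac monitoring are provided in Table 4". The First Dose Cardiac Monitoring text in 9.4.2.1 also states Stop B as mandatory.

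**The concern.** The Day 2 bullet is mandatory and covers every subject who needs extended monitoring on Day 1. Some of those subjects fall under an equally mandatory rule to stop. Read in order, the Extended Cardiac Monitoring bullets look like a complete algorithm: call the Medical Monitor at about Hour 8, redose on Day 2, and stop only if Day 2 also fails. Section 5.1 requires something else.

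What is at stake is a second dose given to a subject who has already met a cardiac stop rule. Protocol 1.3 names first-dose bradycardia and atrioventricular block among the events reported with this drug class, and the Day 1 stops are there to prevent re-exposure in such subjects.

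**Working it through.** No arithmetic beyond timing applies. The check is whether the rules can all be obeyed for the same subject.

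**Inputs**

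- Extended-monitoring set: all subjects who fail Table 3 at Hour 4 (Protocol 9.4.2.1). Failure means a heart rate below 50 bpm that is also more than 10 bpm under baseline, second-degree or higher AV block, or cardiac symptoms.
- Stop A: Table 3 still failed after at least 4 hours of extended monitoring (Section 5.1, Table 4). Timing: Hour 4 + 4 hours = about Hour 8.
- Stop B: the symptomatic event with a heart rate or ECG change during the 4-hour period (Section 5.1, Table 4, and the First Dose Cardiac Monitoring text).
- Redosing rule: the whole extended-monitoring set returns for dose 2 (Day 2 bullet).

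**Overlap**

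- Stop A lies wholly inside the extended-monitoring set, since a subject must be in extended monitoring to meet it. Every Stop A subject therefore gets both orders.
- Stop B overlaps the set only in part. A Stop B subject who meets Table 3 at Hour 4 never enters extended monitoring, and the Day 2 bullet does not apply. A Stop B subject who fails Table 3 at Hour 4 gets both orders.

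**The four logical cases within the extended-monitoring set**

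| Case | Stop B event | Criteria met by about Hour 8 | Day 2 bullet | Section 5.1 / Table 4 | Result |
|---|---|---|---|---|---|
| 1 | No | Yes | Redose | No stop | Consistent |
| 2 | No | No | Redose | Stop A | Conflict |
| 3 | Yes | Yes | Redose | Stop B | Conflict |
| 4 | Yes | No | Redose | Stops A and B | Conflict |

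Three of the four cases conflict. These are logical cells, not frequencies, and two of the three need a Stop B event.

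**Testing an exception**

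- Limiting redosing to subjects who meet the discharge criteria within 4 hours of extended monitoring clears cases 2 and 4 but leaves case 3: 1 of 4 still conflicts.
- Limiting it to subjects not discontinued under Section 5.1/Table 4 clears all three: 0 of 4 conflict.

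**The case against.** The best answer is that the documents largely settle the matter. Section 5.1 is mandatory, and 9.4.2.1 points to it as the full list of reasons to stop. Table 4 repeats both stops shortly after the Day 2 bullet. Stop B is stated before the extended-monitoring text begins, and the neighbouring symptomatic-event bullet excludes Stop B events from its own Day 2 return. A careful reader would let the specific stop prevail over the general bullet. All of this stands, and it is why the point is modest.

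The Medical Monitor is a further safeguard. Contact is expected before a subject is discontinued, Table 4 asks that all discontinuations be discussed, and Section 9.1 sends immediate safety concerns to the Medical Monitor at once. This stands in part. The first two apply only once a site has decided to stop, and the third depends on the site recognising a concern. The Hour 8 contact bullet reaches Stop A subjects, but not a Stop B subject who recovers between Hours 4 and 8.

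The consequence of a misreading is also limited. The subject would stay under monitoring until the discharge criteria were met, and the second dose would be monitored with its own stop at 4 hours. That lowers the risk without removing it, because the Day 1 stops are meant to prevent that dose.

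**Conclusion.** The inconsistency is real. The Day 2 bullet contradicts the mandatory stop for every subject who still fails the discharge criteria after at least 4 hours of extended monitoring. It contradicts the symptomatic-event stop only for subjects who also fail the Hour 4 criteria. It is a low-frequency fault in a safety instruction. It does not affect the sample size, the endpoints or the analysis. Calling it low-frequency is a judgement from the narrow conditions required, since the documents give no event rate.

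A reader might infer three stronger claims, none of which the documents support:

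- *That the protocol intends or permits redosing after a cardiac stop.* The stops are plainly intended and appear in more than one place.
- *That every symptomatic-event stop is contradicted.* Subjects who meet Table 3 at Hour 4 are outside the Day 2 bullet.
- *That a correction made at Amendment 2.0 could have reached at most 225 − 45 = 180 subjects.* The 45 in Protocol 10.2 counts only randomized subjects who fail amended Inclusion Criterion 5, not all those already randomized. Section 9.4.2.1 also applies first-dose monitoring when treatment is restarted after a qualifying interruption, so subjects already randomized may be reached as well. No usable bound follows.

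**What to change.** Amend two bullets under Extended Cardiac Monitoring in Protocol 9.4.2.1.

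1. In the Day 2 bullet, after the reference to requiring extended monitoring on Day 1, insert: *and who is not discontinued from study treatment per Section 5.1/Table 4*. Leave the rest unchanged.
2. In the preceding Medical Monitor bullet, state that subjects who do not meet the criteria after at least 4 hours of extended monitoring are discontinued per Table 4 after contact with the Medical Monitor, and that monitoring continues until the criteria are met.

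The Holter footnote to Table 6 refers back to Section 9.4.2.1 and needs no separate edit. The cost is a short wording amendment, IRB/IEC submission before implementation (Protocol 11.2) and a notice to sites. Data collection, sample size and analysis stay as they are.

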9.4.3. Enrollment in Open-Label Extension Study APD334-303

At the Week 12 assessment a determination will be made regarding continuation into the 40-Week Treatment Period or eligibility for entry into the OLE (Section 5.1.1).

Subjects who discontinue treatment prematurely should have an ET visit as indicated in the Schedule of Assessments (Appendix 1, Table 6). If the ET visit is within 4 weeks of the last proctosigmoidoscopy and biopsy, these procedures do not need to be repeated.

The Day 1 visit of the OLE study must occur within 14 days of the last on treatment visit of this study. In the event there is a gap between the last on treatment visit and W0/D1 of the OLE, the subject should continue their double-blind study medication from Study APD334-210 until the day before the W0/D1 visit. Additional double-blind study medication may be dispensed, if required.

9.5. Follow-Up Period

For subjects not participating in the OLE study, follow-up visits will be performed at 2 and 4 weeks after the last administration of study treatment as indicated in the Schedule of Assessments (Appendix 1, Table 6).

If the ET or Study Completion visit is ≥ 2 weeks after the last administration of study treatment, the 2-Week Follow-Up visit is not required; however, the 4-Week Follow-Up visit should be scheduled and completed. If the ET or Study Completion visit is ≥ 4 weeks after the last administration of study treatment, the 4-Week Follow-Up visit is not required.

If the absolute peripheral lymphocyte count is not within normal limits at the 4-Week Follow-Up visit, subjects should return for CBC with differential according to local standard of care (captured as subsequent Follow-Up visit or unscheduled visit).

All adverse events should be recorded for 30 days after last administration of study treatment (Section 9.9.9.2.2).

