Subjects who discontinue treatment prematurely, regardless of the reason, should be instructed to return for an ET visit within 7 days of the last administration of study treatment (Appendix 1, Table 6) and before initiation of any new treatments to complete all of the ET assessments. If a subject discontinues due to pregnancy, they are not required to complete the endoscopy. If the ET visit is within 4 weeks of the last sigmoidoscopy and biopsy, these procedures do not need to be repeated.

If the ET visit is ≥ 2 weeks of the last administration of study treatment, the 2-Week Follow-Up visit is not required; however, the 4-Week Follow-Up visit should be scheduled and completed. If the ET visit is ≥ 4 weeks of the last administration of study treatment, the 4-Week Follow-Up visit is not required unless the absolute lymphocyte count (ALC) is not within normal limits.

If treatment discontinuation is considered an adverse event, refer to Section 9.9.9.3 for AE/SAE reporting guidance.

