9.8.5. Efficacy-Related Biomarkers

Samples for biomarker assessments will be collected according to the Schedule of Assessments (Appendix 1, Table 6). Blood, tissue, and stool samples will be analyzed by the central or specialty laboratory. Details for collection, processing, and storage will be provided in the Laboratory Manual. Residual samples will be stored and may be used for additional analyses if the subject has granted consent where allowed by the regulatory authorities and local ethics committees.

C-reactive protein (CRP): CRP is an acute phase protein expressed by hepatocytes in response to inflammatory cytokines and will be assessed using a hs-CRP assay. Investigators will be blinded to the hs-CRP results during the treatment and follow-up periods.

Fecal calprotectin: Fecal calprotectin is a complex consisting of calcium-binding proteins. It is expressed by activated neutrophils (and to a lesser extent by macrophages and monocytes) and fecal levels correlate with the number of neutrophils in the gut. It is used as a biomarker of intestinal inflammation. Investigators will be blinded to the fecal calprotectin results during the treatment and follow-up periods.

[figure not shown]
Lymphocyte counts: Etrasimod is believed to modulate lymphocyte trafficking resulting in a reduction in peripheral lymphocyte count and lymphocyte availability for recruitment to sites of inflammation. During the treatment period, the Investigator will be blinded to the white blood cell (WBC) and differential counts during the treatment and follow-up periods. During the treatment period, WBC differential results will be assessed by an unblinded Medical Monitor (not providing direct medical oversight of study conduct). If either of the following occur, the unblinded Medical Monitor will notify the Investigator with additional instructions.

- ANC < 1000 cells/μL
- ALC < 200 cells/μL

If the ANC is confirmed below the 1000 cells/μL limit, the Investigator will be requested to closely monitor for serious infection and institute appropriate follow-up at his or her discretion.

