If the ALC is confirmed below the 200 cells/ μ L limit, study treatment must be interrupted and should not be re-initiated if the ALC remains below this threshold. In this situation, the unblinded Medical Monitor will notify the Investigator and provide instructions on additional actions that the Investigator may need to take. When there is at least one measurement of ALC < 200 cells/ μ L, blinded values may be released to treating physicians and Investigators as deemed medically necessary to monitor infection and/or aid in diagnostic work-up as clinically indicated, and/or as a tool to assess the effectiveness of therapeutic interventions for an infection. Investigators will repeat CBC with differentials weekly until ALC > 500 cells/ μ L.

Re-initiation of the study treatment can only be considered when ALC > 500 cells/ μ L.

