9.9.8. Clinical Laboratory Tests

Refer to Table 5 for the list of clinical laboratory tests to be performed and the Schedule of Assessments (Appendix 1, Table 6) for timing and frequency for each test. Details regarding clinical laboratory sample collection, preparation, and shipment are provided in the Laboratory Manual by the central laboratory.

Clinical safety laboratory tests should be completed pre-dose. The Investigator must review the laboratory report, document this review, and record any clinically relevant changes occurring

during the study in the adverse event section of the eCRF. Results of the total WBC and ALC will be reviewed and monitored as described in Section 9.8.5. The laboratory reports must be filed with the source documents. Clinically significant abnormal laboratory findings are those that are not associated with the underlying disease, unless judged by the Investigator to be more severe than expected for the subject's condition.

All laboratory tests with values considered clinically significantly abnormal during participation in the study or within 30 days after the last administration of study treatment should be repeated until the values return to normal or baseline or are no longer considered clinically significant by the Investigator or Medical Monitor.

- If such values do not return to normal/baseline within a period of time judged reasonable by the Investigator, the etiology should be identified, and the Sponsor should be notified.
- All protocol-required laboratory assessments, as defined in the Schedule of Assessments (Appendix 1, Table 6), must be conducted in accordance with the Laboratory Manual.
- If laboratory values from non-protocol-specified laboratory assessments performed at the institution's local laboratory require a change in subject management or are considered clinically significant by the Investigator (eg, adverse event, SAE, or dose modification), then the results must be recorded in the eCRF.

For guidance on monitoring subjects with notable lymphopenia, refer to Section 9.8.5.

Table 5: Clinical Laboratory Tests

SCREENING ONLY

Virology

HIV, HBsAg, HCV (RIBA)

Stool Sample

Bacterial culture, ova and parasites, C. difficile

Drugs of Abuse

Amphetamine, barbiturates, benzodiazepines, cocaine, methadone,

methamphetamine, methylenedioxymethamphetamine, opiate, oxycodone,

phencyclidine

Others

Hemoglobin A1C, QuantiFERON

PREGNANCY TESTING

Serum pregnancy test β-hCG - Screening

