- Study Completion visit is ≥ 2 weeks after the last administration of study treatment, the 2-Week Follow-Up visit is not required; however, the 4-Week Follow-Up visit should be scheduled and completed. If the ET or Study Completion visit is > 4 weeks after the last administration of study treatment, the 4-Week Follow-Up visit is not required. If the absolute peripheral lymphocyte count is not within normal limits at the 4-Week Follow-Up visit, subjects should return for CBC with differential according to local standard of care (captured as subsequent Follow-Up visit or unscheduled visit).
- d Medical history, including prior and ongoing medication use, will be collected during screening and should be updated for any new conditions or medications as needed prior to dosing at the D1 visit (Section 9.3.6).
- A chest X-ray taken within the previous 6 months from the Screening Visit may also be used.
- f All subjects will complete TB screening to determine eligibility (refer to Appendix 2). The QuantiFERON TB Gold and tuberculin skin test should not be performed in subjects previously diagnosed with TB infection. The TB questionnaire will be completed for all subjects during the Screening Period and at every study visit for subjects residing in countries with a high TB burden or MDR TB as identified by the WHO. For subjects who are receiving TB prophylaxis treatment, the TB questionnaire will be completed at every study visit (until TB prophylaxis treatment course is completed). The TB test is not required at the ET visit.
- 5 Subjects will be tested for HIV antibodies as well as HBV and HCV infection at screening (Section 9.9.8.1.3).
- Subjects will begin eDiary entries the first day of screening after eDiary training is completed. The eDiary should be completed daily to capture data, including daily SF and RB. (the 2 subject-reported outcome measures contributing to the calculation of the MMS and TMS), and study treatment administration. The subject eDiary will be reviewed by study site staff at each treatment visit.
- ⁱThe PGA will be present in source documentation and the eCRF at specified study visits.

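### A subject with low lymphocytes off drug can miss the repeat count that Section 9.5 intends, because the visit rules disagree and the site is blinded to the trigger

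*Protocol*

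**What the plan says.** **Visit rules.** Protocol Section 5.1 covers premature discontinuation. For an ET visit 4 weeks or more after the last dose it says "the 4-Week Follow-Up visit is not required unless the absolute lymphocyte count (ALC) is not within normal limits". Section 9.5 covers ET and Study Completion visits at the same distance and has no such exception. Nor does the Table 6 footnote in Appendix 1: "4 weeks after the last administration of study treatment, the 4-Week Follow-Up visit is not required". Both 9.5 and that footnote then give the repeat-count rule: "If the absolute peripheral lymphocyte count is not within normal limits at the 4-Week Follow-Up visit, subjects should return for CBC with differential". The repeat follows local standard of care.

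**Blinding.** Section 9.8.5 says "the Investigator will be blinded to the white blood cell (WBC) and differential counts during the treatment and follow-up periods". That sentence opens by referring to the treatment period and closes by naming both periods, so it is not cleanly drafted. Table 5 footnote b, however, keeps investigators blinded to lymphocytes after randomization with no end date. Section 9.1 sends protocol laboratory tests to a central laboratory unless otherwise stated.

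**Review and notice.** Section 9.8.5 continues: "During the treatment period, WBC differential results will be assessed by an unblinded Medical Monitor". That monitor notifies the Investigator when ANC is < 1000 or ALC is < 200 cells/µL. Once there has been an ALC < 200, "blinded values may be released to treating physicians and Investigators as deemed medically necessary to monitor infection", and CBC is repeated weekly until ALC exceeds 500. Table 5 footnote a places the unblinded review after randomization, provides for instructions to the site in significant lymphopenia, and refers to 9.8.5 for details.

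**General laboratory rule.** Section 9.9.8 calls for repeats of "All laboratory tests with values considered clinically significantly abnormal during participation in the study or within 30 days after the last administration". On lymphocytes, the same section says "Results of the total WBC and ALC will be reviewed and monitored as described in Section 9.8.5".

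**The concern.** The protocol wants a subject whose lymphocytes have not recovered off drug to be recalled for another count. For a late ET visit, one section keeps the visit on which this depends and two places remove it. More generally, the person who must recall the subject is not allowed to see the result that triggers the recall.

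At stake is safety follow-up. A subject with lymphocytes still below normal could leave the study with no later count showing recovery. SAP Section 6.3.2.1 reports lymphocytes < 0.5 × 10^9/L as markedly abnormal, including at follow-up, so such a count could be tabulated as a finding without the site having had any stated notice to recheck it.

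**Working it through.** There is no planned figure to reproduce. The check is a comparison of texts, with a few unit conversions.

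**1. Visit rules: ET visit ≥ 4 weeks off drug with an abnormal ALC at that visit**

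| Source | 4-Week visit | Further counts called for |
|---|---|---|
| Section 5.1 | kept | at least 1 |
| Section 9.5 | waived | 0 |
| Table 6 footnote | waived | 0 |

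In the last two rows the repeat depends on a count at the 4-Week visit, so waiving the visit removes the trigger as well. In the text as read from PDF, the Table 6 footnote has > 4 weeks where 9.5 has ≥ 4 weeks. They differ only at exactly 4 weeks, and the sign may be a reading artefact. The missing exception does not depend on it.

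Reach: Section 5.1 instructs an ET visit within 7 days of the last dose. The conflict needs one at 4 weeks or later: 4 × 7 = 28 days, and 28 − 7 = 21 days beyond the instruction. For an ET visit before 4 weeks, 9.5 keeps the 4-Week visit and there is no conflict.

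**2. Repeat-count trigger: first off-drug ALC from 200 cells/µL up to the lower limit of normal**

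| Stated route | When it acts | Reaches this subject? |
|---|---|---|
| Site sees the count | blinded through follow-up (9.8.5; Table 5 footnote b) | no |
| Monitor notice (9.8.5) | ALC < 200 or ANC < 1000 cells/µL | not on ALC |
| Release of values, weekly CBC (9.8.5) | after at least one ALC < 200 | no |
| Table 5 footnote a | significant lymphopenia, no limit given, refers to 9.8.5 | not assured |
| Repeat rule (9.9.8) | value judged clinically significant; ALC review sent to 9.8.5 | not assured |

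The 9.5 condition is met and the site cannot see it. No row gives notice at the lower limit of normal. The 5.1 exception relies on the same hidden count. Section 9.8.5 also ties the monitor's review to the treatment period, so only footnote a supports applying even the < 200 notice during follow-up.

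**3. Limits on one scale** (1 L = 10^6 µL)

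- SAP lower cut-off: 0.2 × 10^9 / 10^6 = 200 cells/µL, equal to the notice limit.
- SAP upper cut-off: 0.5 × 10^9 / 10^6 = 500 cells/µL.
- Marked in the SAP but without notice: 200–499 cells/µL.
- Repeat under 9.5: any count outside normal limits. The documents do not give the lower limit.

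**The case against.** The other side has several fair points.

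- **Compatible visit rules.** Section 5.1 can be read as the specific, more cautious rule. A visit that 9.5 calls not required is not forbidden, so a site following 5.1 breaches nothing. True, but a site working from 9.5 or the Table 6 schedule would also breach nothing by omitting it.
- **Wider routes.** Footnote a has no end date and no numeric limit. Section 9.9.8 runs to 30 days after the last dose and gives the Medical Monitor a say in when repeats stop. A repeat could come about this way, but only by judgement: neither text sets notice at the lower limit of normal, and both point to 9.8.5.
- **Strength of the rule.** Section 9.5 says subjects should return, which is softer than a strict requirement. This stands, but an intended repeat still needs someone to know it is due.
- **Planned data.** CBC with differential is scheduled at both follow-up visits, and the SAP tabulates the lymphocyte shift from end of treatment to each of them. This covers recovery up to the 4-Week visit. It cannot show recovery after a low count there.
- **Different purposes.** A SAP reporting cut-off and a clinical action limit need not agree. The mismatch is not itself an error; it shows which counts would be reported without notice.
- **Too many notices.** Entry allows lymphocytes of 0.8 × 10^9/L (800 cells/µL). If the lower limit of normal is above that, which the documents do not say, some subjects would be recalled at their own baseline. This is a real cost, but one already contained in the 9.5 rule.

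**Conclusion.** Both parts hold. For an ET visit 4 weeks or more off drug with an abnormal ALC, Section 5.1 conflicts with 9.5 and Table 6. Separately, the repeat-count rule depends on a value withheld from the site, with no stated notice for a first off-drug ALC from 200 cells/µL up to the lower limit of normal.

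The weight is low. The conflict arises only with very late ET visits. The gap can apply to any subject not entering the extension, but the documents give neither that number nor the frequency of low off-drug counts. Section 1.3 reports counts within normal limits by 7 days after the last dose in earlier studies; if that carries over, few subjects are involved. Low counts would still appear in the planned listings. What may be missing is the later count showing recovery. Efficacy, power and type I error are unaffected.

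The conclusion assumes that the 5.1 exception refers to the ALC at the ET visit, that follow-up counts are run centrally under the blind, and that no site manual outside these documents supplies the missing notice.

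**What to change.** - In Section 9.5 and the Table 6 footnote, add the 5.1 exception for an abnormal ALC.
- Tie the repeat CBC to the last off-drug count, whether it comes from an ET, Study Completion or follow-up visit.
- In Section 9.8.5, state that the unblinded Medical Monitor also reviews follow-up counts. When an off-drug ALC is below normal, the monitor tells the site that a repeat CBC is needed, without giving the value.

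No new SAP output is needed, because the planned listings already flag out-of-range values at all timepoints. If follow-up is already complete, the sponsor can still check which low off-drug counts have no later count.

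The cost is wording in two sections and one footnote, plus a small task for the unblinded monitor. The drawback is that a repeat notice may hint at treatment assignment. Efficacy assessments (Week 52 or ET) are complete by then, but causality judgements on adverse events recorded up to 30 days after the last dose could still be influenced.
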